ANNEX 3. ADDITIONAL INFORMATION

See Appendix 1.

Appendix 1. ICD and MedDRA Codes For Select Safety Endpoints

	ARTIS		BIOBADASER, BSRBR, RABBIT
Event	Operationalization	Validation ICD	Operationalization (Final list TBD based on reported endpoints)
Serious infections	Hospitalizations in the Patient Register listing as main diagnosis ICD10-codes below. If main diagnosis is RA, contributory diagnoses are also considered. A00-B99 (excluding A33 and A50), D73.3, E32.1, G00-G02, G04.2, G05-G07, H00.0, H44.0, H60.0-H60.3, H66-H67, H70, I30.1, I40.0, J00-J22, J32, J34.0, J36, J39.0-J39.1, J44.0, J85, J86, K04.4, K04.6, K04.7, K10.2, K11.3, K12.2, K14.0, K57.0, K57.2, K57.4, K57.8, K61, K63.0, K65.0, K65.1, K65.2, K65.9, L00-L08, L30.3, M00-M01, M46.2-M46.5, M60.0, M65.0, M71.0, M71.1, M72.6, M86, N13.6, N15.1, N15.9, N30.0 N30.8, N34.0, N41.2, N43.1, N45.2, N45.3, N45.4, N48.2, N61, N70, N73, N75.1.	This algorithm has not been specifically validated in ARTIS, but the register itself is subject to strict quality assurance routines and has been validated several times. Refs: Ludvigsson et al. External Review and Validation of the Swedish National Inpatient Register, BMC Public Health, 2011 (11):450. http://www.socialstyrelsen.se/re gister/halsodataregister/patientr egistret/inenglish.	Hospitalization and/or use of parenteral antibiotics+ MedDRA Infections and Infestations SOC 10021881.

	ARTIS		BIOBADASER, BSRBR, RABBIT
HZ reactivation	Hospitalizations in the Patient Register listing as main diagnosis ICD10-codes B00 and B02. If main diagnosis is RA, contributory diagnoses are also considered.	The algorithm used to identify this endpoint in ARTIS has not been validated and is expected to only identify the most severe cases.	10019974 Herpes zoster, 10019983 Herpes zoster ophthalmic, 10030865 Ophthalmic herpes zoster, 10058428 Herpes zoster multi-dermatomal, 10063491 Herpes zoster oticus, 10065038 Herpes zoster disseminated, 10065119 Necrotising herpetic retinopathy, 10072210 Genital herpes zoster, 10074241 Varicella zoster gastritis, 10074245 Herpes zoster pharyngitis, 10074248 Herpes zoster meningoencephalitis, 10074253 Herpes zoster necrotising retinopathy, 10074254 Varicella zoster pneumonia, 10074259 Herpes zoster meningitis, 10074297 Herpes zoster cutaneous disseminated.

	ARTIS		BIOBADASER, BSRBR, RABBIT
CV risk	Major Acute Cardiovascular Events (MACE), combines MI, stroke, and fatal cardiovascular events: 100-199 as main cause of death, or 120.0, 121, 160-164 as diagnosis in in- or outpatient care.	See Serious Infections 'Outcome' was defined as any first-ever ACS event, which in turn was defined as a primary discharge diagnosis of acute myocardial infarction or unstable angina pectoris, or as acute myocardial infarction being the underlying cause of death. For discharge diagnoses, the date of admission to hospital was considered the event date. This outcome definition has previously been validated in a Swedish early RA cohort, with a positive predictive value of 95% [15]. In addition, a regional validation study of hospitalized acute MI and stroke found positive predictive values of 96% and 94% respectively, in the period 1977 to 1987. Lindblad et al. Validity of register data on acute myocardial infarction and acute stroke. Scandinavian Journal of Public health 1993; 21 (1):3-9.	Fatal and non-fatal 10000891 Acute myocardial infarction; 10006147Brain stem infarction; 10006148 Brain stem ischaemia; 10008034 Cerebellar infarction; 10008088 Cerebral artery embolism; 10008120 Cerebral ischaemia; 10008190 Cerebrovascular accident; 10014498 Embolic stroke; 10019005 Haemorrhagic cerebral infarction; 10019016 Haemorrhagic stroke; 10024033 Lateral medullary syndrome; 10028596 Myocardial infarction; 10028602 Myocardial necrosis; 10033697 Papillary muscle infarction; 10043647 Thrombotic stroke; 10049768 Silent myocardial infarction; 10051078 Lacunar infarction; 10055677 Haemorrhagic transformation stroke; 10056237 Migrainous infarction; 10059613 Stroke in evolution; 10060839 Embolic cerebral infarction; 10060840 Ischaemic cerebral infarction; 10061256 Ischaemic stroke; 10062573 Brain stem thrombosis; 10064961 Thalamic infarction; 10066591 Post procedural stroke; 10066592 Post procedural myocardial infarction; 10067167 Cerebellar embolism; 10067347 Thrombotic cerebral infarction; 10067462 Millard-Gubler syndrome; 10068621 Cerebellar ischaemia; 10068644 Brain stem stroke; 10069020 Basal ganglia infarction; 10070671 Cerebral septic infarct; 10070754 Inner ear infarction; 10071043 Basal ganglia stroke; 10071260 Carotid angioplasty; 10073945 Perinatal stroke; 10074422 Brain stem embolism; Fatal only 10002886 Aortic aneurysm rupture; 10003173 Arterial rupture; 10003210 Arteriosclerosis; 10003212 Arteriosclerosis moenckeberg-type;;10006145 Brain stem haemorrhage;;10007556 Cardiac failure acute; 10007559 Cardiac failure; 10007559 Cardiac failure congestive; 10007559 Cardiac failure congestive; 10007686 Carotid arteriy aneurysm; 10007688 Carotid artery thrombosis; 10008023 Cerebellar artery thrombosis; 10008030 Cerebellar haemorrhage;

	ARTIS		BIOBADASER, BSRBR, RABBIT
			10008076 Cerebral aneurysm ruptured syphilitic; 10008086 Cerebral arteriovenous malformation
			haemorrhagic; 10008089 Cerebral artery occlusion; 10008092 Cerebral artery thrombosis; 10008111 Cerebral
			haemorrhage; 10008118 Cerebral infarction; 10008132
			Cerebral thrombosis; 10018985 Haemorrhage
			intracranial; 10022758 Intracranial aneurysm; 10022840 Intraventricular haemorrhage; 10022841 Intraventricular
			haemorrhage neonatal; 10024119 Left ventricular failure;
			10024242 Leriche syndrome; 10034476 Pericardial
			haemorrhage; 10036511 Precerebral artery occlusion;
			10039163 Right ventricular failure; 10039330 Ruptured
			cerebral aneurysm; 10042316 Subarachnoid haemorrhage; 10042434 Sudden death; 10047279
			Ventricle rupture; 10048380 Aneurysm ruptured;
			10048761 Atrial rupture; 10049418 Sudden cardiac
			death; 10049993 Cardiac death; 10050403 Carotid artery
			dissection; 10051093 Cardiopulmonary failure; 10051328 Carotid aneurysm rupture; 10052019 Femoral
			artery occlusion; 10053633 Cerebellar artery occlusion;
			10053649 Vascular rupture; 10053949 Vascular
			pseudoaneurysm ruptured; 10055803 Haemorrhage
			coronary artery; 10058178 Aortic occlusion; 10060874
			Aortic rupture; 10060953 Ventricular failure; 10060964 Arterial haemorrhage; 10062585 Peripheral arterial
			occlusive disease; 10062599 Arterial occlusive disease;
			10063081 Acute left ventricular failure; 10063082 Acute
			right ventricular failure; 10063083 Chronic left
			ventricular failure; 10063084 Chronic right ventricular failure; 10064595 Haemorrhagic arteriovenous
			malformation; 10064601 Iliac artery occlusion; 10065441
			Venous haemorrhage; 10065558 Aortic arteriosclerosis;
			10067057 Basal ganglia haemorrhage; 10067116 Carotid
			arteriosclerosis; 10068119 Aortic dissection rupture;
			10068119 Aortic dissection rupture; 10068230 Cardiorenal syndrome; 10069694 Brachiocephalic artery
			occlusion; 10069695 Subclavian artery occlusion;
			10069696 Coeliac artery occlusion;10071716 Vertebral
			artery dissection; 10072043 Central nervous system
			haemorrhage; 10072789 Iliac artery rupture; 10073565 Intracranial artery dissection; 10073565 Intracranial
I	1	1	intracramal artery dissection; 100/3303 intracranial

ARTIS	BIOBADASER, BSRBR, RABBIT
	artery dissection; 10073681 Epidural haemorrhage; 10075449 Brachiocephalic arteriosclerosis; 10076203 Radiation associated cardiac failure.

	ARTIS		BIOBADASER, BSRBR, RABBIT
GI perforation	Hospitalizations in the Patient Register listing ICD10-codes: K22.3, K25.1, K25.2, K25.5, K25.6, K26.1, K26.2, K26.5, K26.6, K27.1, K27.2, K27.5, K27.6, K28.1, K28.2, K28.5, K28.6, K31.6, K35.0, K35.1, K57.0, K57.2, K57.4, K57.8, K63.0, K63.1, K63.2.	See Serious Infections; Pharmacoepidemiol Drug Saf. 2011 Nov;20(11):1150-8. doi: 10.1002/pds.2215. Epub 2011 Aug 27. Validation of ICD-9-CM codes to identify gastrointestinal perforation events in administrative claims data among hospitalized rheumatoid arthritis patients.	10000099 Abdominal wall abscess; 10000285 Abscess intestinal; 10000582 Acquired tracheo-oesophageal fistula; 10002156 Anal fistula; 10002157 Anal fistula excision; 10002248 Anastomotic ulcer perforation; 10002924 Aorto-duodenal fistula; 10003012 Appendicitis perforated; 10009995 Colonic fistula; 10013536 Diverticular fistula; 10013538 Diverticulitis; 10013541 Diverticulitis intestinal haemorrhagic; 10013828 Duodenal fistula; 10013832 Duodenal perforation; 10013849 Duodenal ulcer perforation; 10013849 Duodenal ulcer perforation; 10013850 Duodenal ulcer perforation, nobstructive; 10017815 Gastric perforation; 10017835 Gastric ulcer perforation; 10017836 Gastric ulcer perforation, obstructive; 10017866 Gastritis haemorrhagic; 10017877 Gastrointestinal fistula; 10017954 Gastrointestinal gangrene; 10017955 Gastrointestinal haemorrhage; 10018001 Gastrointestinal perforation; 10021305 Ileal perforation; 10021310 Ileal ulcer perforation; 10022647 Intestinal fistula; 10022694 Intestinal perforation; 10022647 Intestinal fistula; 10022694 Intestinal perforation; 10023804 Large intestine perforation; 10030181 Oesophageal perforation; 10034354 Peptic ulcer perforation; 1003497 Perforated peptic ulcer perforation; 1003497 Perforated peptic ulcer oversewing; 10034649 Peritoneal abscess; 10034674 Peritonitis; 10038073 Rectal perforation; 10038975 Retroperitoneal abscess; 10041103 Small intestinal perforation; 10046274 Upper gastrointestinal haemorrhage; 10048946 Anal abscess; 10048947 Rectal abscess; 10049583 Douglas' abscess; 10048947 Rectal abscess; 10049583 Douglas' abscess; 10049764 Appendiceal abscess; 10050362 Anovulvar fistula; 10050953 Lower gastrointestinal haemorrhage; 10052211 Oesophageal rupture; 10052457 Perineal abscess; 10052488 Oesophageal ulcer perforation; 10052814 Perirectal abscess; 10050368 Paraoesophageal abscess; 100503691 Enterocolonic fistula; 10056992 Oesophagobronchial

	ARTIS		BIOBADASER, BSRBR, RABBIT
PML	Hospitalizations in the Patient Register listing ICD10-codes: A81.2.	See Serious Infections.	fistula; 10058381 Oesophageal fistula repair; 10059175 Intestinal haemorrhage; 10060921 Abdominal abscess; 10061248 Intestinal ulcer perforation; 10061249 Intra-abdominal haemorrhage; 10061820 Diverticular perforation; 10061975 Gastrointestinal ulcer perforation; 10062065 Perforated ulcer; 10062070 Peritonitis bacterial; 10062570 Enterovesical fistula; 10065713 Gastric fistula; 10065879 Gastrointestinal anastomotic leak; 10066870 Aorto-oesophageal fistula; 10066892 Rectourethral fistula; 10067091 Gastropleural fistula; 10068792 Gastrosplenic fistula; 10071647 Infectious peritonitis. TBD based on reported events.
NMSC	Identified through the Cancer register as all malignancies with ICD-O/2 code C44, and all basal cell cancers recoded in the register's subcomponent on basal cell cancers Alt: all invasive NMSC, identified as non-benign ICD-O/2 code C44, and no basal cell cancers.	About 99% of cancers have been morphologically verified. Reporting of incident cancers (including invasive malignancies as well as cancer in situ) is mandatory and semi automated, resulting in an estimated coverage greater than 95%.	10004146 Basal cell carcinoma; 10004178 Basosquamous carcinoma; 10004179 Basosquamous carcinoma of skin; 10006059 Bowen's disease; 10007390 Carcinoma in situ of skin; 10064055 Lip squamous cell carcinoma; 10063693 Malignant neoplasm of eyelid; 10040808 Skin cancer; 10055115 Skin cancer metastatic 10041834 Squamous cell carcinoma of skin
Malignancy	All invasive malignancies recorded in the cancer register, excluding NMSC.	See NMSC.	Malignant or unspecified tumours (SMQ).

Document Approval Record

Document Name: A3921317_PROTOCOL_RABBIT PASS v1.0 21 August 2019

Document Title: A3921317_PROTOCOL_RABBIT PASS v1.0 21 August 2019

Signed By:	Date(GMT)	Signing Capacity
[name]	26-Aug-2019 10:34:21	Final Approval
[name]	26-Aug-2019 12:17:46	EUQPPV Approval

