The risk of infections among RA patients depends on the environmental distribution of the organism of interest, inherent patient characteristics and treatment for RA. Persons with RA ≥65 years of age are found to be at increased risk of serious infections relative to those <65 years of age in both clinical trial and observational data. The mechanism by which infection risk is increased in RA patients is likely to be multifactorial. In addition to the underlying disease (RA), therapies used to treat the disease have suppressive effects on the immune system. For example, TNFi may affect host defense against infection since TNF mediates inflammation and modulates cellular immune response. To facitinib inhibits cytokines that are integral to lymphocyte activation, proliferation, and function, and inhibition of their signaling may thus result in modulation of multiple aspects of the immune response.

Risk of infections is reportedly higher among TNFi-treated patients than those on DMARDs, ^{4,8,9,20} however studies looking at TNFi-treated cohorts over time have shown that rates of serious infection decline over time.^{3,23} The decline may reflect a change in the risk profile of the population as a result of at-risk patients switching therapies, reduced co-administration of corticosteroids, in addition to any impact of TNFi therapy on overall health.²³

Tuberculosis (TB) is the most common opportunistic infection (OI) in the RA population, with risks approximating 10-20 times that of the general population, likely due in part to RA therapy.^{2,6,7}

Studies comparing the background risk of herpes zoster in RA and general population cohorts have been inconsistent, with some showing no increased risk and some showing modestly elevated risk. ^{10,21,24,28}

Serious infections, including tuberculosis and herpes zoster are important identified risks for RA patients taking tofacitinib.

Malignancies

Certain types of cancers may occur in higher frequency in patients with RA, regardless of the treatment modality, including Hodgkin's and non-Hodgkin's lymphoma, leukemia, myeloma, and lung cancer. ^{18,22} In addition, malignancies, including lymphomas, are a concern with all therapeutic agents that treat RA by modulation of the immune system.

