9.3.3 Endpoints

Endpoints in RABBIT derive from physician reports of the occurrence of any AE or event of special interest. The events of interest, based on previously identified risks in the treated and untreated RA population, include:

- 1. Serious infections (excluding TB): pneumonia, other infections of the respiratory system, infections of the CNS, sepsis, bone or joint infections, OI, other infections.
- 2. TB.
- Herpes Zoster.
- 4. Cardiac disorders: heart failure, coronary artery disease, myocardial infarction, other cardiac disorders.
- 5. Hematologic disorders: bone marrow depression and hypoplastic anaemia, decreased white blood cells, platelet disorders, other blood dyscrasia.

- Disorders of the nervous system (excluding infections): stroke, central demyelination, other disorders of the CNS, disorders of the peripheral nervous system, psychiatric disorders.
- 7. Progressive multifocal leukoencephalopathy.
- 8. Allergic conditions and hypersensitivity.
- 9. Hepatic failure.
- 10. Gastrointestinal (GI) perforations.
- 11. Pregnancy.
- 12. Thromboembolic events: deep vein thrombosis (DVT) and pulmonary embolism (PE).
- 13. Operations and hospitalisations: bone and joint surgery and other joint therapeutic procedures, other operations and (major) therapeutic procedures that lead to hospitalization.
- 14. Other serious diagnoses, symptoms, and syndromes.
- 15. NMSC.
- 16. Malignancies, excluding NMSC.
- 17. All-cause Mortality.

Rates of these endpoints of interest and their 95% CI will be reported for tofacitinib exposed and comparator cohorts every six months.

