The feasibility of conducting a final comparative study will be evaluated at 7-years of follow up based on statistical power and suitable overlap in patient populations in the exposure groups. Any final comparative report will adjust for differences in severity of disease and other confounders will be completed using appropriate multivariate, propensity score matching, or inverse probability weighting methods. For these analyses, the exposure cohorts will be analyzed overall, previous biologics use and monotherapy and combination therapy with concomitant conventional synthetic disease modifying antirheumatic drugs (csDMARDs). A combination therapy with MTX specifically will be described if sample sizes are sufficient. These and potentially other agreed upon strata will be determined apriori and included in SAP filed with Sponsor. The general analytic approach will be descriptive and include rates of events of interest within stratified treatment cohorts. Data will be presented as number of events, crude and age/sex-standardized incidence rates. Such analyses will be performed by and at the direction of RABBIT. The final report will also evaluate the rates of safety events of interest within the elderly. The approved SAP will also describe the a priori determined common set of MedDRA codes and the MedDRA version to define serious infections, GI perforations, herpes zoster, and CV events (MACE). The codes and version will be harmonised with other registers conducting similar analysis. A draft set of MedDRA codes is included in Appendix 1.

Meta-analytic methods that attempt to combine the results of this study with results from other participating European registers will be used to summarize the findings across studies. A quantitative meta-analysis would permit an estimate of an average effect across the studies with more statistical power than the individual studies, provided a formal evaluation did not reveal substantial heterogeneity. Meta-analysis may reveal between-study heterogeneity such that a subset of more comparable studies could be included in a single estimate. Heterogeneity may be expected, for example due to differences in local prescribing practices, patient populations, competing risks, and prevalence of comorbidities and risk factors. Such heterogeneity would exist even if the coding for endpoint definitions and reporting could be harmonized across registers. In the presence of such heterogeneity, pooling across the

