registers is not informative as the generalizability of such an estimate is unknown. Pending feasibility of comparative analysis, meta-analytic methods will be determined a prior and described in an approved SAP.

Detailed methodology for summary and statistical analyses of data collected in this study will be documented in a statistical analysis plan (SAP), which will be dated, filed and maintained by the sponsor. The SAP may modify the plans outlined in the protocol; any major modifications of primary endpoint definitions or their analyses would be reflected in a protocol amendment.

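### Appendix 1 counts ICD-10 B00 (herpes simplex) as herpes zoster in the ARTIS column, which would mislabel events if ARTIS zoster results are compared or pooled with RABBIT's

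*Protocol*

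**What the plan says.** The endpoint list in section 9.3.3 of the protocol names "Herpes Zoster" as its own item. Section 7 gives the reason: "Serious infections, including tuberculosis and herpes zoster are important identified risks for RA patients taking tofacitinib".

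Appendix 1 gives case definitions by register. In the HZ reactivation row, the ARTIS (Swedish register) cell reads "Hospitalizations in the Patient Register listing as main diagnosis ICD10-codes B00 and B02". It adds that contributory diagnoses also count when RA is the main diagnosis. The validation cell beside it says: "The algorithm used to identify this endpoint in ARTIS has not been validated and is expected to only identify the most severe cases".

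The BIOBADASER/BSRBR/RABBIT cell is a MedDRA list that begins "10019974 Herpes zoster, 10019983 Herpes zoster ophthalmic, 10030865 Ophthalmic herpes zoster, 10058428 Herpes zoster multi-dermatomal" and runs to 15 terms.

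On use across registers, section 9.8 says "Meta-analytic methods that attempt to combine the results of this study with results from other participating European registers will be used" to summarise findings, and then sets a condition: "Pending feasibility of comparative analysis, meta-analytic methods will be determined a prior and described in an approved SAP". The same section commits the SAP to a common code set for several endpoints, herpes zoster among them, to be harmonised with the other registers. It calls the MedDRA codes in Appendix 1 a draft.

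**The concern.** One row label covers two different case definitions. The ARTIS cell admits a second disease, caused by a different virus, under the name of zoster. The MedDRA cell does not.

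The caveat in the row does not cover this. It warns that milder cases will be missed, which is a matter of sensitivity. Counting another disease is a matter of specificity, and a reader who relied on the caveat would take every ARTIS event to be severe zoster.

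At stake is how any cross-register reading of an identified tofacitinib risk is interpreted. Simplex admissions would be reported as zoster, the ARTIS rate would be too high for what it claims to measure, and a ratio from ARTIS would mix two diseases. Section 9.8 already expects heterogeneity between registers even with harmonised coding. A coding mismatch adds more, and this part is avoidable.

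**Working it through.** This is a check of definitions. The protocol states no figure on this point, so there is none to reproduce.

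**Step 1: the two cells side by side.**

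| | ARTIS | BIOBADASER/BSRBR/RABBIT |
|---|---|---|
| Coding | ICD-10 B00 and B02 (read as either code) | 15 MedDRA terms |
| Zoster content | B02 | 14 terms naming herpes zoster or varicella zoster |
| Other content | B00, herpes simplex | 1 term, necrotising herpetic retinopathy |
| Herpes simplex named | Yes, through B00 | No |
| Setting | Hospitalisation only | No restriction stated in the cell |

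The meaning of B00 comes from the ICD-10 classification that the column itself names. The protocol does not spell it out, and nothing in the protocol explains why B00 is included.

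**Step 2: what is lost if B00 is removed.** The ARTIS serious infections row covers A00-B99, excluding only A33 and A50. It uses the same rule of main diagnosis, or contributory diagnosis if RA is the main one. Every B00 admission that the HZ row would count therefore already falls under ARTIS serious infections.

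**Step 3: illustration of the effect on an ARTIS result.** Inputs:

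- f, the share of comparator-cohort events under B00 or B02 that are B00. Assumed 10% to 50%; not in the documents.
- RR_z, the zoster rate ratio. Set to 2, borrowed from the two-fold difference used in section 9.6, which is not stated there for zoster.
- RR_s, the simplex rate ratio. Assumed 1; not in the documents.

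Formulas:

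- Observed ratio = (1 - f) × RR_z + f × RR_s
- Inflation of the comparator rate = 1 / (1 - f)
- Inflation of the tofacitinib rate = [(1 - f) × RR_z + f × RR_s] / [(1 - f) × RR_z]

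| f | Observed ratio | Comparator inflation | Tofacitinib inflation |
|---|---|---|---|
| 10% | 0.9×2 + 0.1×1 = 1.90 | 1/0.9 = 1.11 | 1.90/1.80 = 1.06 |
| 30% | 0.7×2 + 0.3×1 = 1.70 | 1/0.7 = 1.43 | 1.70/1.40 = 1.21 |
| 50% | 0.5×2 + 0.5×1 = 1.50 | 1/0.5 = 2.00 | 1.50/1.00 = 1.50 |

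**Step 4: what the illustration depends on.** Observed ratio minus RR_z equals f × (RR_s - RR_z). The bias is towards 1 in the table only because RR_s was set below RR_z. If simplex also doubled, the ratio would stay at 2.0. If the simplex ratio exceeded the zoster ratio, the observed ratio would be too high. The absolute rate labelled zoster is inflated whenever any B00 event is counted.

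With B02 alone, f = 0 and the ARTIS ratio is the ratio for hospitalised zoster.

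**The case against.** The strongest reply is that this is another study's definition. Protocol A3921317 is confined to RABBIT, and B00 is not in RABBIT's cell. ARTIS has its own study, A3921314. A reader might infer from the row that RABBIT's zoster rates, its six-monthly and interim reports, or its comparison with bDMARDs are contaminated. The documents do not support that: no RABBIT patient is classified by these ICD codes.

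A reader might also infer that a biased pooled zoster estimate is already built into the plan. That goes too far. The meta-analysis depends on feasibility and on a formal look at heterogeneity, it may be restricted to a more comparable subset of studies, and its text names no endpoint. Herpes zoster appears in section 9.8 only in the sentence about the common code set.

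A third reply is that the codes are provisional and will be harmonised in the SAP. This stands only in part. The draft label attaches to the MedDRA set, and the note that the final list is still to be determined heads the BIOBADASER/BSRBR/RABBIT column. Neither is attached to the ARTIS ICD cell. The harmonisation commitment does reach the mismatch, but that is a reason to correct the code before it is carried forward. A code stated wrongly is different from detail left to the SAP.

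Finally, the ARTIS cell is already flagged as unvalidated, and the hospital-only restriction makes the two registers' rates non-comparable in any case. That is true, and removing B00 does not cure it. It is a separate problem.

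**Conclusion.** The point holds in a limited form. The ARTIS zoster definition includes a herpes simplex code, which matches neither the protocol's endpoint nor the other registers' cell in the same row, and no reason is given. The consequence is confined to any side-by-side reading or pooling of ARTIS and RABBIT zoster results.

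The size is not known. The range of 1.90 to 1.50 for a true zoster ratio of 2 rests on an assumed B00 share of 10% to 50% and an assumed simplex ratio of 1. The inflation of 1.11 to 2.0-fold applies to the comparator cohort; under the same assumptions the tofacitinib cohort's rate is inflated less, 1.06 to 1.50-fold. It would be tempting to say that the error hides a zoster effect, or that it creates a false one. The documents give neither the B00 share nor the simplex ratio, so neither direction can be claimed.

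**What to change.** Delete B00 from the ARTIS cell of the HZ reactivation row so that B02 alone defines zoster there. Carry the same definition into the harmonised code set in the SAP and into the ARTIS study's own definition, since editing this appendix alone would not change what the Swedish study counts. Leave B00 under ARTIS serious infections, where A00-B99 already covers it. If there was a reason for including B00, state it, relabel the endpoint accordingly, and still report B02 alone for any pooling.

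The cost is one code in an appendix plus coordination with the ARTIS study. No new data are needed. ARTIS would have fewer events under this heading. The hospital-only restriction in ARTIS remains and should be stated wherever the two registers' zoster rates appear together.

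### The draft RABBIT code list in Appendix 1 counts bleeding, diverticulitis and superficial anal or abdominal-wall terms as GI perforation, and decides whether a survived stroke is a MACE by which near-synonym was coded

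*Protocol*

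**What the plan says.** Protocol Section 9.3.3 names gastrointestinal perforations as an endpoint (item 10) and promises six-monthly rates for every listed endpoint. Section 9.8 leaves the final MedDRA codes for GI perforation and MACE to the SAP, says they will be harmonised with other registers, and calls the Appendix 1 set a draft. The header of the RABBIT column in Appendix 1 says the final list is still to be determined.

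**GI perforation row, RABBIT column.** The list opens with "10000099 Abdominal wall abscess; 10000285 Abscess intestinal". It includes "10013538 Diverticulitis; 10013541 Diverticulitis intestinal haemorrhagic", "10017955 Gastrointestinal haemorrhage; 10018001 Gastrointestinal perforation" and "10046274 Upper gastrointestinal haemorrhage; 10048946 Anal abscess". No condition is attached. The serious-infection row of the same column does attach one: hospitalisation and/or parenteral antibiotics.

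**CV risk row.** The ARTIS cell describes MACE as MI, stroke and fatal cardiovascular events, and counts the range "160-164 as diagnosis in in- or outpatient care" without requiring death. The RABBIT cell has two blocks. The first counts fatal and non-fatal events and includes "10071260 Carotid angioplasty". The second begins "Fatal only 10002886 Aortic aneurysm rupture" and includes "10008118 Cerebral infarction; 10008132" followed by cerebral thrombosis, together with the terms named as intracranial haemorrhage.

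Section 9.2 says RABBIT codes events at MedDRA preferred-term level.

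**The concern.** A code list is the working definition of an endpoint. Used as printed, this one would count a GI bleed, an uncomplicated diverticulitis or an anal fistula operation as a GI perforation. The rate published under that name would then be too high in every cohort. Any excess of true perforations on tofacitinib would be mixed with events that may have nothing to do with the drug.

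For MACE the trouble is inconsistency. Two patients who survive the same kind of stroke can be classified differently because one report was coded to a generic term and the other to a more specific one. That loses events from an endpoint already short of power: Table 1 gives 0.41 to 0.47 for 500 tofacitinib patients at 6/1000 PY, even with no switching.

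**Working it through.** The protocol states no figure that depends on these lists, so there is none to reproduce. The check is a reading of the lists plus one dilution calculation.

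**1. GI list sorted by name** (RABBIT column, duplicates collapsed; the list runs across a table break into the PML row).

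| Group | Distinct terms |
|---|---|
| Perforation or rupture | 25 |
| Haemorrhage or haemorrhagic | 7 |
| Diverticulitis | 2 (one also in the haemorrhagic group) |
| Abscess | 12 |
| Fistula | 19 |
| Peritonitis | 3 |
| Gangrene, anastomotic leak | 2 |

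Non-perforation terms: 7 + 2 − 1 + 12 + 19 + 3 + 2 = 44. Total: 25 + 44 = 69. These are counts of terms, not of events.

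**2. Dilution of a perforation rate ratio.** Let k be the ratio of non-perforation to perforation events in the comparator, and assume the drug does not affect the former. Then

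observed RR = (RR + k) / (1 + k).

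The comparator rate is inflated by the factor 1 + k. The protocol gives no value for k, so a range is assumed.

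| k (assumed) | True RR 3 | True RR 2 | Comparator rate inflated by |
|---|---|---|---|
| 1 | (3+1)/2 = 2.0 | (2+1)/2 = 1.5 | 2 |
| 2 | (3+2)/3 = 1.67 | (2+2)/3 = 1.33 | 3 |
| 4 | (3+4)/5 = 1.4 | (2+4)/5 = 1.2 | 5 |

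**3. MACE terms set side by side** (RABBIT column).

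| Counts when survived | Counts only when fatal |
|---|---|
| Ischaemic, embolic, thrombotic and haemorrhagic cerebral infarction | Cerebral infarction |
| Brain stem thrombosis | Cerebral thrombosis |
| Haemorrhagic stroke | Cerebral, subarachnoid, intracranial, brain stem, cerebellar and basal ganglia haemorrhage |

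Each right-hand entry is a more general or neighbouring name for what stands on the left. With coding at preferred-term level, the coder's choice decides whether a survived stroke counts. The ARTIS cell draws no such line.

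**4. Size of the MACE loss.** The fraction lost is (share of MACE that are strokes) × (share of strokes that are both survived and coded to a fatal-only term). The protocol gives neither share. It also does not say which definition lies behind the 6/1000 PY in Section 9.6, which it attributes to earlier register analyses, so any loss may already be in that figure. No number follows.

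**The case against.** The strongest reply is that Appendix 1 is openly provisional. Section 9.8 assigns the a priori codes to the SAP, and nothing is mismeasured until a list is fixed. This stands as a limit: it would be wrong to say the study's endpoints are already misclassified. It does not remove the point. The terms are printed content that the SAP would inherit, and Appendix 1 is the only operational definition in the protocol. Six-monthly rates and interim reports to EMA are scheduled, and the protocol does not say which codes they use. The column header also ties the final list to reported endpoints, which is a reason to settle terms by name before events are seen.

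Four stronger readings are tempting, and the protocol does not support them:

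- *MACE counts infarction and haemorrhage only when fatal.* Cerebrovascular accident, ischaemic and haemorrhagic stroke and many specific infarction terms count when survived. The fault is the placement of some terms.
- *A definite share of MACE is lost.* Supposing that strokes are 40% of MACE and that half are survived and coded to fatal-only terms gives 20%, and takes 6 to 4.8/1000 PY. Both shares would be invented. If coding habits are alike across cohorts, the loss costs precision more than it biases a ratio. Stroke is also reported separately (Section 9.3.3, item 6).
- *The cross-register meta-analysis is undermined.* RABBIT, BIOBADASER and BSRBR share one column, pooling is conditional, and heterogeneity is expected. The stroke rule does differ from ARTIS. For GI perforation, the ARTIS codes carry no labels, so a difference is not shown.
- *All 44 non-perforation terms are wrong.* Deep abscess, fistula and peritonitis terms can plausibly mark a perforation; how to treat them is partly a matter of choice.

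**Conclusion.** The concern holds for the draft list as printed, conditional on its being carried forward. The GI perforation row admits haemorrhage-only, unqualified diverticulitis and superficial anal and abdominal-wall terms that do not denote perforation, with no condition to screen them out. If those events are unrelated to drug, a perforation rate ratio moves toward 1: a true 3 becomes 1.4 to 2.0 for k between 4 and 1. The size rests on the assumed k. If the drug also changes the rate of the other events, the distortion could differ in size or direction.

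The MACE row handles near-synonyms for survived stroke inconsistently, departs from the stroke component stated in the same row, and includes a procedure. The direction is a loss of survived strokes; the amount cannot be computed from the protocol.

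**What to change.** Edit Appendix 1 before any rates are reported under it and before the SAP fixes the codes.

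- **GI perforation, primary definition:** keep the perforation and rupture terms. Remove gastrointestinal, upper, lower, intestinal and intra-abdominal haemorrhage, haemorrhagic gastritis, both diverticulitis terms that lack perforation, and the superficial anal, perineal and abdominal-wall terms (for example anal fistula, anal fistula excision, anal abscess and abdominal wall abscess).
- **GI perforation, sensitivity definition:** the deeper abscess, fistula and peritonitis terms may be kept here as a broader set. This avoids relying on case-by-case confirmation: the queries in Section 9.3.2 name GI ulcers and perforations only, and Section 9.10 says not all events can be verified.
- **MACE:** move generic cerebral infarction, cerebral thrombosis and the intracranial haemorrhage terms, including subarachnoid, to the fatal-and-non-fatal block. Remove carotid angioplasty. Arterial occlusion terms need a stated decision, since an occlusion is not by name a stroke.
- **Other registers:** make the same edits for BIOBADASER and BSRBR; changing RABBIT alone would break their present agreement.

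The cost is fewer GI events, hence wider intervals for that rate, and coordination across the registers. No new data collection is needed.
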